	

- Patients requiring a third controller for their asthma will be considered eligible for this study, and it should also be used for at least 3 months with a stable dose <math>\geq 1</math> month prior to Visit 1.

 
B) Pre-bronchodilator forced expiratory volume (FEV1) <math>\leq 80\%</math> of predicted normal for adults and <math>\leq 90\%</math> of predicted normal for adolescents at Visits 1 and 2, prior to randomization.
 
C) Asthma Control Questionnaire 5-question version (ACQ-5) score <math>\geq 1.5</math> at Visits 1 and 2, prior to randomization.
 
D) Reversibility of at least 12% and 200 mL in FEV1 after the administration of 200 to 400 mcg albuterol/salbutamol or levalbuterol/levosalbutamol (2 to 4 inhalations of albuterol/salbutamol or levalbuterol/levosalbutamol, or of a nebulized solution of albuterol/salbutamol or levalbuterol/levosalbutamol, if considered as a standard office practice) before randomization.
 
E) Must have experienced, within 1 year prior to Visit 1, any of the following events:
 

- Treatment with a systemic steroid (oral or parenteral) for worsening asthma at least once.

- Hospitalization or emergency medical care visit for worsening asthma.

 
Exclusion Criteria:
 

• Patients <12 years of age or the minimum legal age for adolescents in the country of the investigative site, whichever is higher (For those countries where local regulations permit enrollment of adults only, subject recruitment will be restricted to those who are <math>\geq 18</math> years of age).

• Weight is less than 30 kilograms.

• Chronic obstructive pulmonary disease (COPD) or other lung diseases (eg, idiopathic pulmonary fibrosis, Churg-Strauss Syndrome, etc) which may impair lung function.

• A subject who experiences a severe asthma exacerbation (defined as a deterioration of asthma that results in emergency treatment, hospitalization due to asthma, or treatment with systemic steroids at any time from 1 month prior to the Screening Visit up to and including the Baseline Visit).

• Evidence of lung disease(s) other than asthma, either clinical evidence or imaging [eg, Chest X-ray, computed tomography (CT), Magnetic resonance imaging(MRI)] within 12 months of Visit 1 as per local standard of care.

• Note for Japan: According to the request from the health authority, chest X-ray should be performed at screening visit if there is no chest imaging (Chest X-ray, CT, MRI) available within 3 months prior to screening to exclude patients with suspected active or untreated latent tuberculosis.

• Current smoker or cessation of smoking within 6 months prior to Visit 1.

• Previous smoker with a smoking history >10 pack-years.

• Comorbid disease that might interfere with the evaluation of IMP.

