	
adolescent patients will be randomized.
 
Patients will be randomized using a 2:2:1:1 randomization ratio for dupilumab 300 mg q2w, dupilumab 200 mg q2w, placebo q2w in 2 mL and placebo q2w in 1.14 mL.
 
Randomization will be stratified by age (<18 years, ≥18 years) at screening, central eosinophil count (<300 cells/μL, ≥300 cells/μL) at screening, ICS dose level (medium, high) and country.
 
In addition, in order to have additional patients treated with drug manufactured using the intended commercial process, approximately 220 patients will be randomized in addition to the originally planned sample size (1638).
 
Analysis populations:
 
The primary analysis population for the efficacy endpoints will be intent-to-treat (ITT) population defined as all randomized patients. The efficacy analyses will be conducted according to the treatment to which they are randomized.
 
The secondary analysis population for the efficacy endpoints will be HEos (High Eosinophils) ITT defined as all randomized patients with baseline eosinophil count ≥300 cells/μL
 
The analysis population for the safety endpoints will be the safety population, defined as all patients exposed to study medication, regardless of the amount of treatment administered. The safety analyses will be conducted according to the treatment that patients actually received.
 
Analysis of the primary endpoints:
 
The annualized rate of severe exacerbation events will be analyzed using a negative binomial regression model. The model will include the total number of events occurring during the 52 weeks as the response variable, with the treatment group, age, region (pooled country), baseline eosinophil strata, baseline ICS dose level and number of severe exacerbation events within 1 year prior to the study as covariates. Log transformed treatment duration will be the offset variable. Patients who permanently discontinue the study medication will be asked and encouraged to return to the clinic for all remaining study visits and the additional off-treatment severe exacerbation events up to Week 52 will be included in the analysis and the last contact date at Week 52 will be used to calculate the offset variable. The change from baseline in FEV1 at Week 12 will be analyzed using a mixed-effect model with repeated measures (MMRM) approach. The model will include change from baseline FEV1 values up to Week 12 as response variables, and factors for treatment, age, sex, height, region (pooled country), baseline eosinophil strata, baseline ICS dose level, visit, treatment by-visit interaction, baseline FEV1 value, and baseline-by-visit interaction as covariates. An unstructured correlation matrix will be used to model the within-patient errors. Parameters will be estimated using restricted maximum likelihood method using the Newton-Raphson algorithm. Statistical inferences on treatment comparisons for the change from baseline in FEV1 at Week 12 will be derived from the mixed-effect model. For patients discontinuing the treatment before Week 12,

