- h* Prior to screening, patients must be on a stable background therapy of a medium to high dose of inhaled corticosteroid (ICS) in combination with a second controller medication (eg, long-acting beta agonist [LABA], leukotriene receptor antagonist [LTRA], methylxanthine, etc) for at least 3 months with a stable dose  $\geq 1$  month prior to Visit 1. Patients requiring a third controller are allowed to participate in this study. The third controller should also be used for at least 3 months with a stable dose  $\geq 1$  month prior to Visit 1 (patients requiring systemic steroids as controller medication or biologics are excluded).
- i* Every 2 week (q2w) investigational product administrations must be separated by at least 11 days. The randomized Treatment Period visits occur every 2 weeks up to Week 12 and then every 4 weeks, alternating with q2w home administration of IMP (patient, caregiver, or health care professional) without study visit up to the end of treatment period at Week 52. After Week 12, if the patient or Investigator decides not to administer IMP at home, the IMP injections can be performed at the site by way of unscheduled visits. Patients will be monitored at the study site for a minimum of 30 minutes after injections in the first 12 weeks.
- j* Electronic diary/PEF meter is used for daily recording of salbutamol/albuterol or levalbutamol/levolbuterol use, asthma controller drug use, oral steroid requirements, nocturnal awakenings due to asthma symptoms, morning and evening asthma symptom NRS scores and AM and PM PEF. This device is dispensed at Visit 1 and information is downloaded from this device on the other indicated days.
- k* ACQ-7 is completed in the patient's electronic diary during clinic visits. ACQ-7 (Asthma Control Questionnaire 7-question version) score will be used to follow up evaluations in all patients. ACQ-5 (the first 5 items of the ACQ-7) score is used for eligibility evaluation at visit 1 and visit 2 for all patients and follow up evaluations in all patients.
- l* Exhaled nitric oxide assessment is conducted prior to spirometry and following a fast of  $\geq 1$  hour.

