## 7 SELECTION OF PATIENTS

### 7.1 INCLUSION CRITERIA

- I 01. Adults and adolescent patients with a physician diagnosis of asthma for  $\geq 12$  months, based on the Global Initiative for Asthma (GINA) 2014 Guidelines and the following criteria:
- A) Existing treatment with medium to high dose ICS ( $\geq 250$  mcg of fluticasone propionate twice daily or equipotent ICS daily dosage to a maximum of 2000 mcg/day of fluticasone propionate or equivalent) in combination with a second controller (eg, LABA, LTRA) for at least 3 months with a stable dose  $\geq 1$  month prior to Visit 1.
    - Note for Japan: for subjects aged 18 years and older, ICS must be on  $\geq 200$  mcg of fluticasone propionate twice daily or equivalent; for subjects aged 12 to 17 years, ICS must be  $\geq 100$  mcg of fluticasone propionate twice daily or equivalent.
    - Patients requiring a third controller for their asthma will be considered eligible for this study, and it should also be used for at least 3 months with a stable dose  $\geq 1$  month prior to Visit 1.
  - B) Pre-bronchodilator forced expiratory volume ( $FEV_1$ )  $\leq 80\%$  of predicted normal for adults and  $\leq 90\%$  of predicted normal for adolescents at Visits 1 and 2, prior to randomization.
  - C) Asthma Control Questionnaire 5-question version (ACQ-5) score  $\geq 1.5$  at Visits 1 and 2, prior to randomization.
  - D) Reversibility of at least 12% and 200 mL in  $FEV_1$  after the administration of 200 to 400 mcg albuterol/salbutamol or levalbuterol/levosalbutamol (2 to 4 inhalations of albuterol/salbutamol or levalbuterol/levosalbutamol, or of a nebulized solution of albuterol/salbutamol or levalbuterol/levosalbutamol, if considered as a standard office practice) before randomization.
  - E) Must have experienced, within 1 year prior to Visit 1, any of the following events:
    - Treatment with a systemic steroid (oral or parenteral) for worsening asthma at least once.
    - Hospitalization or emergency medical care visit for worsening asthma.
- I 02. Signed written informed consent.

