- Obtain blood sample for ANA test. Note: Anti-ds DNA antibody will be tested if ANA is positive ( $\geq 1:160$  titer).
- Obtain blood sample for serum immunoglobulins (total IgG, IgG subclasses 1-4, IgM and IgA)
- Obtain serum  $\beta$ -HCG pregnancy test if female of childbearing potential
- Obtain urine for urinalysis (dipstick) If any assessment on the dipstick is abnormal, a urine sample should be sent to the central laboratory for testing.
- Dispense electronic diary/PEF meter, provide instructions for daily use, and remind patient to bring the device to the next visit.
- Remind patients to use salbutamol/albuterol or levosalbutamol/levalbuterol as reliever medication throughout the study. Instruct patient to record usage in the electronic diary.

- Remind patient to continue their stable dose of ICS in combination with one or two other controllers as used during the screening period and instruct patient to record daily usage in the electronic diary.
- Remind patient to withhold bronchodilators according to their action duration, for example, withhold last dose of salbutamol/albuterol or levosalbutamol/levalbuterol for at least 6 hours and withhold last dose of LABA for at least 12 hours (ultra-long acting LABA like vilanterol should be withheld for at least 24 hours) and withhold the last dose of LAMA for at least 24 hours prior to next visit.
- Schedule a site visit within 21 to 35 days (Visit 2, Week 0) and request patient to come at approximately the same time of this visit (fasting if morning visit).

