2.1.3 Efficacy endpoints

Baseline for efficacy endpoints is defined as the last non-missing value up to randomization but prior to the administration of the first IMP unless otherwise specified.

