2.4.4.2 Analyses of secondary efficacy endpoints

2.4.4.2.1 Absolute/percent change from baseline for continuous endpoints

The key secondary endpoint, percent change from baseline in pre-bronchodilator FEV1 at Week 12, will be analyzed in the same way as for change from baseline in FEV1 at Week 12, with the only difference that percent changes, instead of absolute changes, from baseline in FEV1 up to Week 12 will be included as the response variables. MMRM model including measurements up to Week 52 will also be used to derive LS mean change at all time-points. Differences in LS means, the corresponding 95% CI and the p-value will be provided for comparisons of each dupilumab dose against its matching placebo along with descriptive statistics.

Change from baseline in ACQ-5 and AQLQ at Week 24 will be analyzed using MMRM including change from baseline up to Week 24 as response variables, regardless if the patient is on treatment or not when the endpoint is measured. The model will include treatment, age, region (pooled country), baseline eosinophil strata, baseline ICS dose level, visit, treatment by-visit interaction, baseline endpoint value, and baseline-by-visit interaction as covariates. MMRM model including measurements up to Week 52 will also be used to derive LS mean change at all time-points. Differences in LS means, the corresponding 95% CI and the p-value will be provided for comparisons of each dupilumab dose against its matching placebo along with descriptive statistics.

Change from baseline in other continuous endpoint at all time-points will be analyzed using MMRM model including measurements up to Week 52. The model will include change from baseline in the endpoint values from Week 2 to Week 52 as response variables, regardless if the patient is on treatment or not when the endpoint is measured, and treatment, age, sex, baseline height, region (pooled country), baseline eosinophil strata, baseline ICS dose level, visit, treatment by-visit interaction, baseline endpoint value and baseline-by-visit interaction as covariates. Sex and baseline height will be included as covariates only in the models for spirometry parameters. Differences in LS means, the corresponding 95% CI and the p-value will be provided for comparisons of each dupilumab dose against its matching placebo along with descriptive statistics.

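### Pre-bronchodilator FEV1 and ACQ-5 are measured at two required visits before randomization, but the models adjust only for the last value; adding the Visit 1 value would probably gain some precision at little cost

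*Protocol*

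**What the plan says.** **Two readings are required.** Inclusion criteria B and C (Protocol 7.1) set the FEV1 and ACQ-5 thresholds "at Visits 1 and 2, prior to randomization". The flow chart footnote in Protocol 1.2 confirms for ACQ-5 that the "score is used for eligibility evaluation at visit 1 and visit 2 for all patients". Protocol 10.1.1 places Visit 2 between 21 and 35 days after Visit 1. SAP Table 9 gives Visit 1 its own window (before Day -14) for pre-bronchodilator spirometry, ACQ-5 and ACQ-7.

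**One reading is used.** SAP 2.1.3 states that the efficacy baseline "is defined as the last non-missing value up to randomization but prior to the administration of the first IMP". In the protocol's Clinical Trial Summary, the covariate list of the FEV1 MMRM ends with the baseline FEV1 "value, and baseline-by-visit interaction as covariates"; Protocol 11.4.2.1 and SAP 2.4.4.1.2 likewise contain one baseline value and its interaction with visit. The sample code in the SAP has a single baseline variable and takes response rows from Visit 3 to Visit 8 only. For ACQ-5 at Week 24, SAP 2.4.4.2.1 likewise lists "baseline endpoint value, and baseline-by-visit interaction as covariates". No planned model uses the Visit 1 value as a second covariate, as part of an average, or as a response.

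**Where these models feed the testing order (SAP Table 6).** FEV1 at Week 12 supplies tests 2, 4, 5, 7, 9, 11, 13, 15, 18, 23, 29 and 30. ACQ-5 at Week 24 supplies tests 21 and 26.

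**The concern.** A single FEV1 or ACQ-5 reading mixes the patient's usual level with visit-to-visit noise. A second pre-randomization reading of the same measure carries more information about that usual level, which age, sex, height and region cannot supply. Unless Visit 1 predicts nothing about Week 12 or Week 24 once Visit 2 is known, leaving it out gives a larger residual variance than the collected data require.

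Fourteen of the 30 ordered tests come from these two measures, and testing stops formally at the first failure. The FEV1 test in the eosinophil ≥0.3 Giga/L subgroup at 300 mg is test 9. It has the lower of the two stated FEV1 powers (88%), and a miss there blocks tests 10 to 30.

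**Working it through.** **Inputs from the documents** (Protocol 11.1; SAP 1.3): SD 0.5 L; 546 versus 273 patients and a difference of 0.15 L overall; 230 versus 115 patients and a difference of 0.18 L for eosinophils ≥0.3 Giga/L; two-sided 5% level.

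**Step 1: reproduce the stated power.** Power = Φ(difference / SE − 1.96), with SE = 0.5 × √(1/n₁ + 1/n₂).

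- Overall: SE = 0.5 × √(1/546 + 1/273) = 0.0371 L; 0.15/0.0371 = 4.05; power 98.2% (stated 98%).
- Subgroup: SE = 0.5 × √(1/230 + 1/115) = 0.0571 L; 0.18/0.0571 = 3.15; power 88.3% (stated 88%).

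**Step 2: variance reduction from a second baseline.** Let r₁₂ be the correlation of Visit 1 with Visit 2, r₂ that of Visit 2 with the outcome, and r₁ that of Visit 1 with the outcome, all after the other covariates. Then:

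- residual variance with Visit 2 only: 1 − r₂²
- residual variance with both: 1 − (r₁² + r₂² − 2·r₁·r₂·r₁₂)/(1 − r₁₂²)

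The correlations below are assumptions; neither document gives any.

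| r₁₂ / r₂ / r₁ | Variance reduction |
|---|---|
| Equal, 0.75 / 0.80 / 0.85 | 18.4% / 19.8% / 21.1% |
| 0.80 / 0.75 / 0.72 | 9.1% |
| 0.85 / 0.80 / 0.77 | 8.1% |
| 0.90 / 0.85 / 0.82 | 5.7% |
| 0.85 / 0.80 / 0.75 | 4.9% |
| 0.80 / 0.75 / 0.68 | 4.1% |
| 0.85 / 0.80 / 0.73 | 2.5% |
| 0.70 / 0.60 / 0.50 | 2.0% |
| 0.85 / 0.80 / 0.68 (Visit 1 adds nothing given Visit 2) | 0% |

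Example, 0.85/0.80/0.73: one baseline leaves 1 − 0.64 = 0.360; two leave 1 − (0.5329 + 0.64 − 0.9928)/0.2775 = 0.351; ratio 0.975. The edges are not sharp: a slower decay, 0.85/0.80/0.78, gives 10.0%.

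**Step 3: selection.** Patients must meet a threshold at both visits, which narrows both readings. In a simulation of three normal readings with equal correlation, keeping only patients below a cut-off on both pre-randomization readings, the reduction was 8-11% at a correlation of 0.6 (14% unselected) and 14-17% at 0.8 (20% unselected).

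**Step 4: effect on power.** With 0.5 L taken as the residual SD of the planned model and a proportional variance cut c, power = Φ((difference/SE)/√(1 − c) − 1.96).

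| c | Subgroup (230 vs 115) | Overall (546 vs 273) |
|---|---|---|
| 0 | 88.3% | 98.2% |
| 2.5% | 89.1% | – |
| 5% | 89.9% | 98.6% |
| 9% | 91.1% | 98.9% |
| 18% | 93.6% | – |

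In patients, a 2.5% cut in the subgroup is worth 345/0.975 − 345 ≈ 9, and a 9% cut 345/0.91 − 345 ≈ 34.

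**The case against.** The strongest reply is that nothing here is defective. Adjusting for the last pre-dose value is pre-specified, legitimate and unbiased. **That stands.** A reader might infer that the FEV1 or ACQ-5 analysis is wrong, or that a loss of precision is demonstrated. The documents support neither, because a gain of zero is possible.

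A reader might also take 18-21% as the expected gain. That needs Visit 1 to predict the outcome as well as Visit 2 does, although it is three to five weeks older, and it ignores selection at both visits. It is an upper case.

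The 88% starting point is debatable too:

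- About 220 extra patients are to be randomized, and the analysis takes all data up to lock. If all of them reached Week 12 by then and 42% were ≥0.3 Giga/L, the arms would be about 260 and 130 (1858 × 0.42 = 780, divided 2:2:1:1). Power would be 91.8% with no model change.
- The 0.5 L is attached to the change in FEV1, not stated as a residual SD. If it is the raw SD of change, with equal variances and a correlation of 0.75-0.85, the planned adjustment multiplies the variance by (1 + r)/2, and power is already 91-92%.

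Both stand as reasons to treat the power gain as modest and conditional.

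The SAP averages a week of diary data for PEF, symptom and reliever baselines. It is tempting to call the single FEV1 reading inconsistent with this. It is not: those are daily entries just before randomization and do not reach back to Visit 1.

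Finally, adding a covariate has pitfalls. The mixed-model procedure drops records with a missing covariate. Eligibility does not guarantee a usable value in the ITT population: SAP 2.2.1 foresees ineligible patients being randomized, and Protocol 9.2.1.1.1 discards unacceptable spirometry manoeuvres. Visit 1 is also the fallback baseline when Visit 2 is missing, so the two covariates would then coincide. These points do not defeat the suggestion, but the fix must deal with them.

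**Conclusion.** The point holds as an efficiency suggestion. Two required pre-randomization readings exist, and the models adjust for one. Using both would probably reduce residual variance: about 2-9% under time-decaying correlations, nothing if Visit 1 is redundant, and up to about 18-21% under equal correlations of 0.75-0.85 before allowing for selection. All of these rest on assumed correlations.

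The visible benefit is in the subgroup FEV1 tests: from 88% to about 89-91% at eosinophils ≥0.3 Giga/L for a 2.5-9% cut, if 0.5 L is the residual SD and the arms are 230 and 115. The overall FEV1 test gains almost nothing from 98%. For ACQ-5 the direction is the same, but the documents give no SD, effect or power, so no gain can be stated. Priority is between optional and recommended; the validity of the results does not depend on it.

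**What to change.** Before unblinding, in SAP 2.4.4.1.2 and 2.4.4.2.1:

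- Keep the last pre-dose value as the baseline for the change score, so that endpoint and estimand are unchanged.
- Add the Visit 1 value (Table 9 window, before Day -14) and its interaction with visit as a second covariate in the MMRMs for pre-bronchodilator FEV1 (absolute and percent change) and for ACQ-5/ACQ-7.
- Carry the same term into the matching multiple-imputation/ANCOVA sensitivity analyses and the subgroup models.
- State which reading counts as Visit 1 when there are several. Protocol 10.1 lets screening span more than one site visit, and Protocol 9.2.1.1.2 allows repeat reversibility tests with a new qualifying FEV1.
- Impute a missing Visit 1 value without reference to treatment, for example by the overall mean or a prediction from baseline covariates, so that no ITT patient is dropped. Say how a patient is handled whose baseline is itself the Visit 1 value.

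The cost is a few extra model parameters, a small SAP edit, and aligning the model wording in Protocol 11.4.2.1, which would go through the usual amendment approval. No new data collection is needed.

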# 1 FLOW CHARTS

## 1.1 GRAPHICAL STUDY DESIGN

Background therapy: medium to high dose ICS plus second controller (LABA, LTRA, etc)  
Third controller is allowed

### 1.2 STUDY FLOW CHART FOR PATIENTS WHO WILL COMPLETE TREATMENT

	S C R a	Randomized Treatment Period																									Post-treatment Period				
		R N D c																								E O T b			E O S		
Week	-4± 1	0	2	4	6	8	10	12	14	16	18	20	22	24	26	28	30	32	34	36	38	40	42	44	46	48	50	52	56	60	64
Visit	1	2	3	4	5	6	7	8		9		10		11		12		13		14		15		16		17		18	19	20	21
Informed Consent	x																														
Incl/Excl Criteria	x	x																													
Patient Demography	x																														
Medical/Surgical History	x																														
Reversibility d	x																														
Post-bronchodilator FEV 1 d		x	x	x		x		x						x						x								x			x
Spirometry e	x	x f	x	x	x	x	x	x		x		x		x		x		x		x		x		x		X		x	x	x	x
CXR or MRI (if none within previous 12 months, MRI is only for Germany) g	x																										X				
Prior & concomitant medication h	x	x	x	x	x	x	x	x		x		x		x		x		x		x		x		x		X		x	x	x	x
Physical Examination	x													x														x			x
Randomization		x																													
Call IVRS/IWRS	x	x	x	x	x	x	x	x		x		x		x		x		x		x		x		x		X		x			x
Investigational Product Administration i		x	x	x	x	x	x	x	x	x	x	x	x	x	x	x	x	x	X	x	x	x	x	x	x	X	x				
Dispense or download e-diary/PEF meter j	x	x	x	x	x	x	x	x		x		x		x		x		x		x		x		x		X		x	x	x	x

	S C R a	Randomized Treatment Period																									Post-treatment Period					
		R N D c																								E O T b	E O S					
Week	-4± 1	0	2	4	6	8	10	12	14	16	18	20	22	24	26	28	30	32	34	36	38	40	42	44	46	48	50	52	56	60	64	
Visit	1	2	3	4	5	6	7	8	9	10	11	12	13	14	15	16	17	18	19	20	21											
Dispense/Review Home Dosing Diary								X		X		X		X		X		X		X		X		X		X		X				
ACQ-7 k	X	X	X	X	X	X	X	X		X		X		X		X		X		X		X		X		X		X	X	X	X	
AQLQ(S)		X						X						X						X								X			X	
Health Care Resource Utilisation		X		X		X		X		X		X		X		X		X		X		X		X		X		X	X	X	X	
Exhaled NO l	X	X	X	X				X		X		X		X						X							X		X	X	X	
Vital Signs m	X	X	X	X	X	X	X	X		X		X		X		X		X		X		X		X		X		X	X	X	X	
ECG	X		X	X				X						X						X								X			X	
Pregnancy test n	X	X		X		X		X		X		X		X		X		X		X		X		X		X		X			X	
Clinical lab testing o	X	X		X		X		X		X		X		X		X		X		X		X		X		X		X	X	X	X	
Hepatitis B viral load p		X						X						X						X								X				
AE/SAE recording	X	X	X	X	X	X	X	X		X		X		X		X		X		X		X		X		X		X	X	X	X	
Urinalysis q	X							X						X						X								X			X	
Serum immunoglobulins (IgG, IgM, IgA)	X							X						X						X								X			X	
Systemic drug concentration (functional dupilumab) r		X	X	X		X		X		X				X						X								X	X	X	X	
Anti-drug antibodies r		X						X						X														X			X	
Biomarker set s		X						X						X						X								X				
Periostin		X		X				X																				X				
Antigen-specific IgE		X						X						X														X				

	S C R a	Randomized Treatment Period																								Post-treatment Period					
		R N D c																							E O T b	E O S					
Week	-4± 1	0	2	4	6	8	10	12	14	16	18	20	22	24	26	28	30	32	34	36	38	40	42	44	46	48	50	52	56	60	64
Visit	1	2	3	4	5	6	7	8	9	10	11	12	13	14	15	16	17	18	19	20	21	22	23	24	25	26	27	28	29	30	
Archival serum f		x						x						x						x								x			
Pharmacogenetics: blood samples for DNA and RNA u		x																													
EQ-5D-5L		x						x						x						x								x		x	
HADS v		x						x						x						x								x		x	
SNOT-22 w		x						x						x						x								x		x	
RQLQ(S) +12 x		x						x						x						x								x		x	
Vaccine IgG	x y				z	z	z	z		z		z		z		z		z		z		z		z		z		z			

- a The Screening Period is 4±1 weeks (21-35 days) in duration to collect baseline data on asthma control and assure eligibility criteria.
- b Patients who permanently discontinue treatment early will continue the remaining visits per protocol schedule with a +/-5 day window until end of study (See section 1.3). At the time of permanent treatment discontinuation the patients will perform early treatment discontinuation (ETD) visit with all the assessments defined for Visit 18 (EOT).
- c Randomization Visit (Visit 2) is defined as Day 1. Visit windows for subsequent visits are +/- 3 days.
- d Three attempts may be made during the Screening Period until the Baseline visit to meet the qualifying criteria for reversibility. During the treatment period, post-bronchodilator FEV1 will be determined at the designated treatment visits. If other attempt for reversibility test was performed at Baseline visit, then the post-bronchodilator FEV1 will come from the result of this reversibility test.
- e Forced expiratory volume (FEV1), PEF, Forced vital capacity (FVC), Forced expiratory flow between 25% to 75% of vital capacity (FEF25%-75%) at all visits; pulmonary function tests should be performed in the morning if possible, but if it could only be done at a different time of the day, the spirometry should be done at approximately the same time of the day at each visit throughout the study. Spirometry will be performed after a wash out period of bronchodilators according to their action duration, for example, withholding the last dose of salbutamol/albuterol or levosulbutamol/levalbuterol for at least 6 hours and withholding the last dose of LABA for at least 12 hours (ultra-long acting LABA like vilanterol should be withheld for at least 24 hours) and withholding the last dose of Long-Acting Muscarinic Antagonist (LAMA) for at least 24 hrs. This will be verified before performing the measurements.
- f Treatment Period stability limits will be established for FEV1 and PEF. Period stability limit for PEF is defined as the respective mean AM or PM PEF obtained over the last 7 days prior to Visit 2 ((Day1). There should be at least 4 days' measurement for setting up the stability limit, and the first dosing visit should be rescheduled until data for 4 days are available.
- g Perform chest X-ray or MRI (MRI is for Germany only) if no chest imaging (X-ray, CT, MRI) available within the previous 12 months as per local standard of care or if there is local requirement. At Visit 17, it is only applicable for patients who plan to participate in the OLE study and available chest imaging is over 12 months from entry into the OLE study.

Note for Japan: According to the request from the health authority, chest X-ray should be performed at screening visit if there is no chest imaging (Chest X-ray, CT, MRI) available within 3 months prior to screening to exclude patients with suspected active or untreated latent tuberculosis.

- h* Prior to screening, patients must be on a stable background therapy of a medium to high dose of inhaled corticosteroid (ICS) in combination with a second controller medication (eg, long-acting beta agonist [LABA], leukotriene receptor antagonist [LTRA], methylxanthine, etc) for at least 3 months with a stable dose  $\geq 1$  month prior to Visit 1. Patients requiring a third controller are allowed to participate in this study. The third controller should also be used for at least 3 months with a stable dose  $\geq 1$  month prior to Visit 1 (patients requiring systemic steroids as controller medication or biologics are excluded).
- i* Every 2 week (q2w) investigational product administrations must be separated by at least 11 days. The randomized Treatment Period visits occur every 2 weeks up to Week 12 and then every 4 weeks, alternating with q2w home administration of IMP (patient, caregiver, or health care professional) without study visit up to the end of treatment period at Week 52. After Week 12, if the patient or Investigator decides not to administer IMP at home, the IMP injections can be performed at the site by way of unscheduled visits. Patients will be monitored at the study site for a minimum of 30 minutes after injections in the first 12 weeks.
- j* Electronic diary/PEF meter is used for daily recording of salbutamol/albuterol or levalbutamol/levolbuterol use, asthma controller drug use, oral steroid requirements, nocturnal awakenings due to asthma symptoms, morning and evening asthma symptom NRS scores and AM and PM PEF. This device is dispensed at Visit 1 and information is downloaded from this device on the other indicated days.
- k* ACQ-7 is completed in the patient's electronic diary during clinic visits. ACQ-7 (Asthma Control Questionnaire 7-question version) score will be used to follow up evaluations in all patients. ACQ-5 (the first 5 items of the ACQ-7) score is used for eligibility evaluation at visit 1 and visit 2 for all patients and follow up evaluations in all patients.
- l* Exhaled nitric oxide assessment is conducted prior to spirometry and following a fast of  $\geq 1$  hour.
- m* Vital signs, including blood pressure (mmHg), heart rate (beats per minute), respiratory rate (breaths per minute), body temperature (degrees Celsius) and body weight (kg) will be measured at the screening and randomization visits (Visits 1 and 2) and every subsequent visit. Height (cm) will be measured only at screening (Visit 1) for adults, and be measured at the screening and randomization visits (Visits 1 and 2) and every subsequent visit for adolescents. Vital signs will be measured in the sitting position using the same arm at each visit, and will be measured prior to receiving investigational product at the clinic visits.
- n* Serum pregnancy test at Visit 1 and urine dipstick pregnancy tests at other visits. A negative result must be obtained at Visits 1 and 2 prior to randomization.
- o* Hematology: hemoglobin, hematocrit, platelet count, total white blood cell (WBC) count with five-part differential count, differential count, and total red blood cell count. Serum chemistry: creatinine, blood urea nitrogen, glucose, uric acid, total cholesterol, total protein, albumin, total bilirubin (in case of values above the normal range, differentiation in conjugated and non-conjugated bilirubin), alanine aminotransferase, aspartate aminotransferase, alkaline phosphatase, lactate dehydrogenase, electrolytes (sodium, potassium, chloride), bicarbonate, and creatine phosphokinase. Clinical laboratory testing at Visit 1 and Visit 17 (only applicable for patients who plan to participate in the OLE study) include hepatitis screen covering hepatitis B surface antigen (HBs Ag), hepatitis B surface antibody (HBs Ab), hepatitis B core antibody (HBc Ab) including HBcAb IgM and total, hepatitis C virus antibodies (HCV Ab), Human Immunodeficiency Virus (HIV) screen (Anti-HIV-1 and HIV-2 antibodies) and anti-nuclear antibody (ANA). In case of results showing HBs Ag (negative), and HBc Ab total (positive), a hepatitis B virus DNA (HBV DNA) testing must be performed prior to randomization to determine eligibility. In case of results showing HCV Ab (positive), a HCV virus RNA (HCV RNA) testing must be performed prior to randomization to determine eligibility. Note: Anti-ds DNA antibody will be tested if ANA is positive ( $\geq 1:160$  titer). The blood sample for serum chemistry must be taken with the patient in fasting state which means no intake of any food or drink except for water for at least 8 hours (if the visit can only be done at a different time of the day and the patient is not fasting, then he/she should be advised to eat light food and the site should document that serum chemistry was not obtained under fasting conditions).
- p* This is only applicable for patients in Japan or other countries/regions if there is local regulatory requirement who are HBs Ag negative and HBs Ab positive at the screening visit.
- q* Urine dipstick analysis including specific gravity, pH, glucose, ketones, blood protein, nitrite, leukocyte esterase, urobilinogen and bilirubin. If any assessment on the dipstick is abnormal, a urine sample should be sent to the central laboratory for testing. If positive for proteins, microscopic analysis will be performed by central laboratory.
- r* Systemic drug concentration and ADA samples are to be collected prior to dosing. In the event of any SAE or any AESI of anaphylactic reactions or systemic allergic reactions that are related to IMP and require treatment, or severe injection site reaction lasting longer than 24 hours, samples will be collected near the onset and resolution of the event for any additional analysis if required or for archival purposes.. See Section 9.3.1 for more details.
- s* Biomarker set includes Eotaxin-3, eosinophil cationic protein (ECP), total IgE, Thymus and Activation-Regulated Chemokine (TARC). Blood eosinophil count will be measured as part of hematology test. Exhaled nitric oxide assessment is described separately in the flowchart.
- t* Archival serum in case needed for retrospective safety follow-up or additional biomarker analysis, and this is optional and a separate written consent form must be signed.
- u* This is optional and a separate written consent form must be signed before sampling. For those who consented, the sample should be drawn at Week 0, before IMP administration.
- v* HADS includes Hospital Anxiety and Depression Scale- Anxiety subscale (HADS-A) and Hospital Anxiety and Depression Scale- Depression subscale.
- w* For those patients with bilateral nasal polyposis and/or chronic rhinosinusitis.
- x* For those patients with comorbid allergic rhinitis.

- y Patients will be encouraged to provide vaccination plans for the following vaccines, tetanus (alone or combined), any injectable influenza, any pneumococcal and any meningococcal, which are in line with the patients age and local medical practice (live attenuated vaccines are excluded) during the study. Subjects planning to receive any of the above listed vaccines during the study may optionally sign a separate informed consent for collection of 2 blood samples for assay of vaccine IgG in serum for each vaccination.
- z Optional collection of blood for assay of vaccine IgG in serum for each vaccine of interest: the first sample should be drawn within 6 weeks prior to vaccination and then the second should be drawn 3 to 4 weeks after vaccination (up to 6 weeks afterward allowed). Vaccinations should preferably occur after completion of at least 12 weeks of treatment, while remaining in compliance with the patient's recommended immunization schedule. Pre-vaccine blood sample collection will not take place until patient is on treatment of IMP for at least 6 weeks. Blood collections should be conducted at regularly scheduled study visits but, if this is not feasible, could also be done at unscheduled visits.

